#### **Laboratory Evaluation**

Blood samples will be collected after an overnight fast. At baseline and months 9 and 18 (key outcome visits), fasting lipid profiles, glucose, AST, ALT, hs-CRP, and creatinine will be measured using standard enzymatic techniques at the Madison VA Clinical Laboratory. APOE genotyping will be determined from coded specimens by resources from the UW ADRC, the UW Biotechnology Center and/or LGC genomics for a fee for service. Genotyping will occur for all participants at the end of the study using blood samples collected and stored from the pre-study visit. This APOE genotype information will be used in analysis. Baseline analysis of CSF samples will be performed at the WI Alzheimer's Disease Research Center - Biospecimen Lab. This analysis will be for specific measures of beta-amyloid and tau. The UW Biospecimen laboratory will not receive any identifiable information on the research participants as the CSF samples will be coded with their unique subject ID and date, and they will not have access to the key. Coded biospecimen data, including DNA samples will be analyzed to determine various SNP (singlenucleotide polymorphism) sequences. CSF Aβ42, Aβ40, T-tau, and p-tau-181 will be measured with Roche elecsys in the UW ADRC Biomarker Laboratory. Pre- and post-therapy samples will all be run simultaneously at the conclusion of the study to reduce laboratory variability. All biospecimen data will be stored in a freezer, within the secured Madison VA's Research Freezer until clinical analyses occur. Access to the freezer is protected by VA access control, and equipped with backup power and a telephone alarm system. The research freezer space can only be accessed by authorized personnel. Participants will be asked for permission to store their blood, DNA and CSF samples for future research purposes, this will be optional. Samples will be stored for banking purposes specified in the BRAVE Repository Protocol (IRB 2017-0013) and used with consistent approval of the banking repository protocol. Samples will be coded. Specifically, vials containing samples will be labeled with subject ID numbers (###). The label will also include the study name, collection site number, study visit number, contents of each collection vial, and the date of collection. Participants will be made aware, through informed consent, that their samples will be stored for future use.

Cognitive Battery (Table 4): At the pre-study visit, participants will be screened for cognitive dysfunction using the CERAD List Learning Task, questions regarding memory concerns, and an assessment of global cognitive function with the Montreal Cognitive Assessment (MoCA). CERAD scores falling 1.5 SD below the mean will trigger a referral for a detailed clinical evaluation and trial enrollment will be deferred until a cognitive disorder can be ruled out. At baseline and months 9 and 18, the ADCS-PACC battery will be administered to all participants following MRI, LP, blood tests, and a light breakfast. As is done in the A4 trial, the same battery will be used at baseline and month 18 and an alternate battery at month 9 to allow cognitive data collection at three time points while reducing practice effect. All cognitive testing will be recorded and stored on an audio recorder within the VA's protected environment until tests are scored. Upon scoring tests, the recorded audio will be deleted. Participants will be screened for depression with the Center for Epidemiologic Studies Depression Scale (CES-D) at baseline and months 9 and 18. The cognitive test battery will be administered by a trained technician in accordance with the ADCS-PACC guidelines. All psychometricians will be trained by an experienced VA neuropsychologist. As the Wisconsin ADRC is a site for the A4 trial, several psychometricians have already been trained and certified in ADCS-PACC administration. Scoring will be completed strictly according to ADCS-PACC guidelines. Changes in the ADCS-PACC composite scores of the intervention group will be compared to changes in the placebo group after adjusting for practice effects, thus, maximizing internal validity and interpretability of cognitive performance across time. The ADCS-PACC includes: 1) the Total Recall score from the Free and Cued Selective Reminding Test (FCSRT) (0-48 words), 2) the Delayed Recall score on the Logical Memory IIa subtest from the Wechsler Memory Scale (0-25 story units), 3) the Digit Symbol Substitution Test score from the Wechsler Adult Intelligence Scale-Revised (0-93 symbols), and 4) the MMSE total score (0-30 points). The composite score is determined from its components using an established normalization method. Each of the four component change scores is divided by the baseline sample standard deviation of that component, to form standardized z scores. These z scores are summed to form the composite.

#### **ADCS-PACC Battery Tests**

Free and Cued Selective Reminding Test (FCSRT): Verbal memory is being measured during this test.

Immediate and Delayed Logical Memory Test: This test measures one's ability to learn and recall verbal information.

Wechsler Adult Intelligence Scale-Revised: During this test, executive function will be measured.

Mini-Mental Status Examination (MMSE): This 30-point examiner-administered questionnaire measures global cognitive function and evaluates orientation, language, reading, attention/concentration, memory, and constructional ability. Although widely used, it is not sensitive to mild cognitive impairment. This test will be administered to evaluate and identify enrollees with significant cognitive impairment. Subjects with significant cognitive impairment will not complete the remainder of the visits.

#### Questionnaires

At baseline and months 9 and 18, a 20-minute, validated 152-item FFQ will be administered to estimate omega-3 fatty acid intake from all food sources. The questionnaire was validated in a Midwestern population and included seafood items that were available in the

Midwestern food supply and, thus, will be similar to food patterns in our population. The questionnaire asks participants about their usual dietary intake over the past month, breaking it down into eight frequency responses. This FFQ has a high reliability (alpha coefficient = 0.83), demonstrating that volunteers are able to estimate and give the same information on intake over time. To evaluate for depression, the Hamilton Depression Rating Scale will be assessed at baseline, 1, 3, 9, and 18 months in all participants. To assess TBI exposure, specific questions from the Department of Defense's "Survey of Health Related Behaviors Among Active Duty Military Personnel" will be used to assess combat and noncombat deployments, exposure to blast-related and other injuries, and associated short-term and long-term symptoms following any injury (i.e. duration of loss of consciousness, amnesia, headache, etc.). In addition, PTSD symptoms will be evaluated using specific items from the same questionnaire assessing traumatic experiences during deployments and sequelae from those experiences. Additional information on depression, dysthymia, anxiety, PTSD, alcohol abuse, and other psychiatric symptoms will be assessed through administration of different portions of the Mini International Neuropsychiatric Interview (MINI) 6.0 at baseline. Drug dependence/abuse will not be assessed in this modified version of the MINI that will be administered to Veterans.

# D) REPORTING STUDY FINDINGS

#### Reporting Findings

If any abnormal clinically-relevant findings are noted on MRI, labs (blood and/or CSF), or cognitive testing, the participant will receive a phone call from the study team and the clinicallyrelevant abnormal findings will be sent to them in a letter. If the participant has consented and signed a release of information form, then we will contact their primary care physician with these results and send them to the PCP as well. Baseline and month 18 MRI scans will be reviewed by a neuroradiologist within a month of the scan, labs within a week of their collection, and all cognitive tests within a month of evaluation. Cognitive test results 1.5 standard deviations below normal will be reviewed by a staff neuropsychologist. CSF and blood tests will not be placed in the participant's chart as it could affect the study blind. MRI scans are research scans and not meant for clinical interpretation, so will not be placed in the VA chart. Participants will be informed of any abnormal cognitive findings and referred for further clinical evaluation of cognitive changes. Thus, while we will not put the cognitive scores in their VA chart, with the participant's authorization we will notify their PCP of the clinical concerns raised by the research cognitive testing and that provider will likely put that in their VA-based note. The following results will be released to Veteran participants following their baseline visits: 1) Lipid panel (total cholesterol, triglycerides, high and low density lipoprotein cholesterol) 2) High-sensitivity c-reactive protein 3) basic metabolic profile (blood glucose, serum creatinine, AST, and ALT) 4) Spinal fluid red blood cell and white blood cell counts 5) Results from urine pregnancy tests. These results will be summarized in a signed letter from one of our clinicians indicating participants' baseline laboratory results and normal/abnormal ranges. They will be instructed to contact their PCP if they have any concerns accompanied with the printed out results. Results for genetic tests will not be released to participants. If a participant is hospitalized or experiences adverse events, a VA clinician will place a note to the PI in the VA CPRS notification system. Study wide results (randomization arm, primary outcome analysis, complete study-wide laboratory values at each blood draw (if participant consented, if not these will be omitted), and any change in cognition over the course of the study) will be communicated with study participants through cover letters and newsletters. Participants will be directed to follow up with their primary care provider if they have any questions about their laboratory values or if they have noticed any memory concerns.

**Potential Risks: Physical** 

**Icosapent ethyl (IPE) or Vascepa (R) use:** Individuals with known allergy to fish oil, fish, or shellfish may experience anaphylactic shock. The most common side effects of icosapent ethyl include constipation, gout, mouth, joint or muscle pain, and swelling of the hands, legs or feet. Some people also have an increased risk of heart rhythm problems, including atrial fibrillation or flutter, requiring hospitalization, especially if they have a history of these problems.

**Fasting** (12 hours for blood draw and/or lumbar puncture): shakiness, nervousness, sweating, dizziness or light-headedness, sleepiness, confusion, difficulty speaking, anxiety, and weakness.

**Blood Draw:** Phlebotomy can be associated with minor ecchymoses, pain, and a small risk of infection. Fainting or light-headedness may also occur.

**MRI:** An MRI presents virtually no risk to healthy individuals without metallic implants. Some patients may experience claustrophobia. The MRI protocol used in the proposed study requires lying on a hard surface for 30 - 60 minutes, which may cause some discomfort. Moreover the scanner is loud. The radio frequency waves used in the MRI have produced burns in about one in a million exams (most of those minor). Other risks of injury due to MRI include damage to implanted electronic devices (such as pacemakers), bleeding if aneurysm clips are present, and trauma if iron-bearing objects are brought too close to the scanner. Risks posed to pregnant women and fetuses from MRI scans are at this time unknown.

**X-Ray Exam:** If an x-ray is done prior to the MRI, the amount of radiation received is small(similar to the amount of background radiation received from living on this planet for about 6 months).

**Lumbar Puncture**: The most common complication of lumbar puncture is post-dural puncture headache. Bacterial meningitis is a very rare complication of lumbar puncture, occurring in fewer than 0.2% in one series. Uncal or tonsillar herniation is a very uncommon complication, occurring in <1% of very high-risk subjects with known primary or metastatic neoplasms who underwent a lumbar puncture. In rare cases, subjects may visit an emergency room after their visit to have a blood patch performed to alleviate the LP headache. A blood patch is an injection of some of the subject's blood into the LP site to patch a spinal fluid leak. This is only done in rare circumstances. As with the blood draw, there is a small risk of infection with a blood patch. There is also a risk of bleeding and lower back discomfort. Lidocaine is used to numb the lower back before the collection of CSF. In rare cases, allergic reactions to lidocaine may occur, which can cause redness and swelling of the skin.

**Cognitive Testing**: Mental fatigue from the cognitive tests is the most common or frequent physical risk expected related to this procedure.

#### Study Drug Formulation, Packaging, Labeling, and Storage

The manufacturing of Vascepa® and matching placebo capsules, along with packaging, bottling, and all the technical and functional activities required at the level of integration to complete these activities will be performed by Amarin Pharma, Inc. under a Material Transfer Cooperative Research and Development Agreement (MT CRADA) established between Amarin Pharma, Inc. and the William S. Middleton Memorial Veterans Hospital, in Bedminster, NJ and Madison, WI respectively. Under an active Investigational New Drug (IND) application all icosapent ethyl and mineral oil placebo capsules for this study have met stability and other product

testing (including dimensional analysis, weight checks of capsules fill color and shell composition, shell characterization, microbial limits, disintegration, and appearance on all active and inactive study medications) sufficient to meet the Food and Drug Administration (FDA) requirements. Amarin Pharma, Inc. the manufacturer of Vascepa®, will transfer all bottled and packaged clinical study medication to the William S. Middleton Memorial Veteran's Hospital Pharmacy department; the latter entity will store the study medication until study medication distribution visits and will be responsible for the study drug randomization of participants. Since Amarin Pharma, Inc. will blind and code study medication bottles, Amarin Pharma, Inc. will provide this coded list to the Madison VA Pharmacy who will keep this information confidential from the PI and study team members until the end of the study when the code is finally disclosed to the study team. Using the code provided by Amarin Pharma Inc., the Madison VA Pharmacy will randomize enrolled participants to either active drug (icosapent ethyl) or placebo (inert mineral oil) medication and dispense study medication at distributed time points outlined in Table 1: Study Design. At the completion of the study, the Madison VA Hospital Pharmacy Department will destroy all unused and leftover medication from the study.

# D) DATA MANAGEMENT, ANALYSIS, AND STATISTICAL CONSIDERATIONS

#### **Data Management**

Personnel will be trained to monitor adherence to the study protocol. All CSF, blood, MRI, and cognitive data will be double entered into a password-protected database on a secure VA server by trained study personnel. Extreme or inconsistent values or data discrepancies will be reviewed by a study biostatistician and an investigator and data will be verified accordingly. Subjects' identifiable information will be stored on paper and in electronic format. The mature, secure web application, known as REDCap will be used as our electronic data management system. This database will be configured by the UW DOM IT to match the VA's version and then transferred to the VA server where some study data will be stored. Therefore, data entered into REDCap will be on a VA server and under VA purview. Database support for REDCap will be provided by the VA IRMS with appropriate cybersecurity measures adhered to. In the event that VA sensitive data is transmitted electronically, information will only be transmitted using VA approved solutions such as FIPS 140-2 or PKI encryption.

Participant contact activity will be recorded in the Contact Registry for Recruitment. Innovation and Education (CoRRIE) database and will be utilized by the study team throughout the course of time that a participant is actively enrolled in the study. CoRRIE is a University of Wisconsin Department of Medicine web-based application based on the Ruby on Rails web development framework. For licensing details see: https://github.com/rails/rails/blob/master/MIT-LICENSE. Access to CoRRIE is further limited to individuals both approved by the CoRRIE dataset custodians (or delegated authorities), and having completed all applicable SMPH HIPAA training. All communication between web clients (internet browsers) and the CoRRIE application takes place via Hypertext Transfer Protocol over Secure Socket Layer (SSL) or HTTPS. HTTPS provide the ability for normal web based communication over an encrypted SSL connection. This ensures that data passing between the client and CoRRIE is protected. The server hosting Corrle is located behind the UW-Madison SMPH firewall. The SMPH firewall does not allow outside (of SMPH network) access to the server itself. Outside access to the CoRRIE application is allowed through a combination of firewall rules, reverse proxy access, and directory level user authentication. BRAVE identifications will be further coded in CoRRIE and the key to re-identify participants will be stored on the VA server. No PHI/PII will be added to CoRRIE for BRAVE participants.

All participant paper documents will be filed in a locked storage cabinet, inside the secured VA GRECC office, a VA protected environment. Participants will be identified by their study ID numbers and only study team members will have access to the source document linking participants to their personal health information. All specimen collected during the course of this study will be labeled with coded study ID numbers unique for each participant. Only coded data will be transmitted securely to others as part of the study process. Coded data will be disclosed to the WI Alzheimer's Disease Research Center - Biospecimen Lab for CSF analyses, the Wisconsin Institute for Medical Research (WIMR) and UW Biotech. In the event of a suspected or actual data breach, the ISO and PO and ACOS for Research will be notified within one hour of any actual or suspected data breach. This includes the unauthorized use, disclosure, transmission, removal, theft, loss or destruction of VA research-related PHI. individually identifiable private information, or confidential information. Research data is not intended to be removed from the VA protected environment. Additionally, data access will be terminated for study personnel when they are no longer part of the research team. Lastly, if research data or information is transmitted electronically, it will be encrypted with FIPS 140-2 validated encryption.

#### Randomization

Subjects who successfully complete all baseline data collection will be randomized by the Madison VA Pharmacy in a 1:1 ratio as previously described, using a forced block design and stratifying based on sex to force balance in this factor.

#### **Analysis Population**

All analyses will be performed on an intent-to-treat basis as far as follow-up allows. All randomized patients will be encouraged to continue to be assessed and, if they consent, included in the analysis regardless of compliance with study medication. Follow-up rates in similar studies conducted by the PI are between 94-97% (see **Preliminary Studies**). We therefore conservatively predict 90% follow-up in this 18-month trial. For patients missing final values (month 18) but having intermediate measurements of outcomes (month 9), final outcomes will be imputed using expectations from longitudinal data analyses conditional on available data, with random noise added using standard errors taken from the residuals of these analyses. Patients missing all post-baseline values will be omitted. Sensitivity analyses will be conducted to quantify potential biasing effects of dropout on estimated treatment effects and multiple imputation used to quantify the additional variation. There will be no formal interim analyses for efficacy as this is a proof-of-concept study and the rCBF and CSF biomarker changes do not have any clearly known clinical consequences at this time.

#### **Analyses**

For imaging analyses, the statistical models prescribed by our ADRC biostatistician can be effected in SPM (including SPM5, SPM8, and SPM12) or AFNI. Analyses will use an empirically predefined statistical region of interest (sROI) to characterize the treatment effect with optimal power and freedom from multiple comparisons as described by Chen and Reiman. The sROI was defined using a training dataset, i.e., an independent longitudinal dataset (baseline and follow-up without treatment) of ASL-CBF maps collected in asymptomatic, middle-aged adults with a parental history of AD. Using a paired-samples voxel-wise t-test in SPM, the training dataset was analyzed for regions of statistically significant CBF declines. The candidate regions for the sROI were selected based on those that best characterized CBF declines in this group in regions implicated in AD pathology. The sROI will then be applied to ASL-CBF maps in the current study, and averaged values from the sROI will be extracted for statistical analysis. The predefined sROI facilitates correction for multiple comparisons and reduces our exposure to Type 1 error by greatly

reducing the number of voxels in the search region that are evaluated. Anatomical ROIs that aligned with the statistically-defined ROI will be examined hierarchically in a priori selected regions of interest in the following order: bilateral posterior cingulate, bilateral precuneus, bilateral medial temporal lobe. Analyses of ROIs will be discontinued if the group difference in 18 month rCBF in the previous ROI is not significant.

The outcomes - rCBF and CSF Aβ42 – were seen to be right skewed based on pilot data; thus, analyses for each specific aim will be conducted on the logarithmic scale so that "mean" refers to the geometric mean outcome. Specific Aim 1 (IPE effects on rCBF) will be addressed with an analysis of covariance on all subjects with 18 month rCBF of the sROI as the outcome, IPE use as a factor, and baseline rCBF as a continuous predictor, with the main hypothesis tested using the coefficient of IPE's effect on mean rCBF. Baseline rCBF is included as a flexible generalization of modeling change in rCBF. The models for Aim 2 (IPE effects on CSF) will take the same form as in Aim 1 except that the endpoints will be CSF AB42 and that we expect the coefficients of IPE to be negative if the alternative hypotheses are true. For exploratory and descriptive purposes, joint longitudinal analyses of baseline, 9, and 18-month outcomes will be conducted using the same model formulations as above and the method of Laird and Ware. Aim 3 is exploratory and will investigate the impact of IPE on 18-month cognitive performance using the constructs proposed for CBF and CSF analyses. The composite ADCS-PACC scores allow for assessment of overall cognitive functioning and a higher level of reliability than is possible with any given individual measure. A linear regression model will be fitted to the raw scores using age, gender, and education as covariates. Using the regression coefficients from this analysis we will calculate predicted scores for each experimental and control subject. The difference between the predicted and observed scores will then be determined for each subject. Relevant statistical graphics will be used to examine all scientific questions.

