
the participant's contact information will be kept in a file in a locked drawer, in a locked office, of a restricted-access section (the VA GRECC) of the VA.

Wisconsin has 436,630 total living Veterans (93% non-Hispanic white, 3.6% African American, 1.3% Hispanic or Latino, 8.6% women) and there are 191,500 Wisconsin Veterans between the study eligibility ages of 50-75 years (44% of total Wisconsin Veterans). The Madison VA Hospital serves 130,000 Veterans living in 15 counties in south-central Wisconsin and in five counties in northwestern Illinois. Assuming that approximately 44% of these Veterans are in the 50-75 year age range (57,200) and that approximately 13% will have a parent with AD (based on AD prevalence estimates for Wisconsin), we estimate that we will have a recruitment pool of approximately 7500 Veterans between the ages of 50-75 years with a parent with AD. Based on the gender and race/ethnicity of Veterans in Wisconsin, we assume that approximately 580 (7.8%) will be women, 270 (3.6%) African American, and 98 (1.3%) Hispanic/Latino.

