Subjects who successfully complete the baseline visit will be randomized in a 1:1 ratio to IPE 4 g (four 1-g gel caps) daily or matching IPE gel cap placebos (four 1-g mineral oil gel caps). Vascepa (IPE) 1 g gel caps will have logos de-inked to match the mineral oil placebo gel caps. Participants will be randomized to either four 1-g Vascepa gel caps daily or four matching 1-g mineral oil gel caps daily. The participant will take 2 capsules (2-g) by mouth twice daily. Amarin will provide all study medication and matching mineral oil gel cap placebos and is responsible for all study drug quality testing, packaging, and distribution of study drugs to the Madison VA Pharmacy research team. Randomization will be conducted by the Madison VA Pharmacy using a forced block design and will be stratified based on gender. Participants, investigators, and other study personnel will be blinded to the identity of the study medications and to lipid-lowering effects of the study drugs.

A clinician not directly involved in data analysis and interpretation will review possible side effects related to IPE at each visit, including liver enzyme monitoring. If adverse lab changes occur, participants will have appropriate safety interventions performed (see Protection of Human Subjects). The VA Psychiatric, Behavioral Health and Neurologic Disorders (PBN) Central Data Monitoring Committee (DMC), VA Hines Hospital, Hines, IL will oversee participant safety monitoring. Potential study drug adverse effects will be collected at each study visit via a questionnaire.

Lumbar puncture adverse effects include post-lumbar puncture (LP) headache at a rate of 5-10% based on clinical data from the literature. Our team has a post-LP headache rate at around 2%. Data on rates of post-LP headaches will be collected to ensure our rates are within the expected range.

Incidental abnormal MRI findings have occurred in our prior studies; thus, a neuroradiologist will review all baseline and month 18 MRI scans for incidental findings of clinical significance. MRI scans will be reviewed by the neuroradiologist within 1 month of the scan.

Cognitive performance will also be evaluated. If participants test 1.5 standard deviations below the normal range, their results will be reviewed with a neuropsychologist to evaluate whether the findings are of clinical significance.

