#### Covariates

Important potential confounding factors for changes in outcome measures will be assessed, including age, sex, APOE4 carrier status (positive/negative), parental history of AD, systolic blood pressure, use of antihypertensive agents, plasma LDL-C and HDL-C levels, bodymass index, waist-hip ratio, exercise frequency, Hamilton Depression Rating Scale score, history of moderate or severe TBI, PTSD, and DHA/EPA intake. In addition, all analyses for cognitive effects will be adjusted for age, sex, and education.

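### Randomisation is stratified by sex, but the Aim 1 and Aim 2 models adjust only for the baseline outcome; adding sex and baseline age would be a minor, low-cost refinement

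*Combined protocol and SAP*

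**What the plan says.** All references are to the combined protocol and SAP.

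- **Design.** Study Protocol (Table 2): "Randomization will be conducted by the Madison VA Pharmacy using a forced block design and will be stratified based on gender". The Randomization section repeats this and gives the reason: "using a forced block design and stratifying based on sex to force balance in this factor".
- **Aim 1 model.** The Analyses section takes log 18-month rCBF as the outcome, with "IPE use as a factor, and baseline rCBF as a continuous predictor, with the main hypothesis tested using the coefficient" of the treatment term.
- **Aim 2 model.** "The models for Aim 2 (IPE effects on CSF) will take the same form as in Aim 1", with CSF Aβ42 as the endpoint.
- **Covariates.** "Important potential confounding factors for changes in outcome measures will be assessed, including age, sex, APOE4 carrier status" and a dozen or so others. This section names no factor as a term in the Aim 1 or Aim 2 model, gives no selection rule, and does not say at which visit the factors are measured. It is definite only for cognition: "all analyses for cognitive effects will be adjusted for age, sex, and education".
- **Expected share of women.** Recruitment gives two figures. For the recruitment pool, "we assume that approximately 580 (7.8%) will be women". For all Wisconsin Veterans, "3.6% African American, 1.3% Hispanic or Latino, 8.6% women".

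**The concern.** A factor that restricts the randomisation would normally appear in the primary model. If it predicts the outcome and is left out, the model-based standard error still contains variation that the design has already balanced, so the test is slightly conservative and some precision is lost. Age is not a stratification factor. It is simply a baseline variable already in hand, in a cohort spanning 50 to 75 years, that may predict either outcome beyond its own baseline value.

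The wording of the Covariates section adds a practical problem. Several listed factors (blood pressure, LDL-C and HDL-C, Hamilton score, dietary DHA/EPA intake) are measured again after randomisation, and Study Protocol itself names LDL-C changes among the possible effects of IPE. Without a rule on timing and role, an analyst could adjust for a post-treatment value, or settle the covariate set after seeing results.

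**Working it through.** **Inputs from Power Calculations.** Two-sided α = 0.05. Aim 1: effect size 0.57, 67 per arm. Aim 2: effect size 0.59, 62 per arm, baseline 778.2 ± 173.2 ng/L, 13% decline against 0%. Retained at month 18: 134 of 150.

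**Assumed, because the documents do not give them.** The partial R² of sex and age given the baseline outcome (0–10%), and the baseline-to-month-18 correlation r (0.3, 0.5, 0.7).

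**Step 1: the plan's own figures.** Power comes from the noncentral t with noncentrality d × √(N/4).
- Aim 1: 0.57 × √(134/4) = 3.299; on 131 df, power = 90.57%. The stated 90% reproduces.
- Aim 2: two-sample t-test, 0.59, 62 per arm: 90.3%. This reproduces too.

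**Step 2: Aim 1 with sex and age added.** Noncentrality = d/√(1 − R²) × √[(N − 3 − q)/(N − 3)] × √(N/4), on N − 5 = 129 df. The middle factor charges for chance imbalance: q = 1 charges age only (sex is balanced by design), q = 2 charges both. Example, R² = 5%, q = 2: 0.57/√0.95 × √(129/131) × √33.5 = 3.359, power 91.52%.

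| Partial R² | Power, q = 2 to q = 1 | Change from 90.57% (points) |
|---|---|---|
| 0% | 90.14–90.35% | −0.4 to −0.2 |
| 1% | 90.42–90.63% | −0.2 to +0.1 |
| 2% | 90.70–90.91% | +0.1 to +0.3 |
| 5% | 91.52–91.72% | +1.0 to +1.2 |
| 10% | 92.86–93.04% | +2.3 to +2.5 |

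The terms pay for themselves above an R² of 0.79% (q = 1) or 1.55% (q = 2).

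These figures take 0.57 as already baseline-adjusted. If it is on the raw scale, d becomes 0.57/√(1 − r²). Planned power is then 92.96%, 96.57% or 99.57% at r = 0.3, 0.5 or 0.7, and the gain at R² = 5% is 0.8–1.0, 0.5–0.6 or 0.1 points.

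**Step 3: sex alone in Aim 1.** Expected women: 134 × 0.078 = 10.5 to 134 × 0.086 = 11.5. For a sex difference of D residual SDs, v = p(1 − p)D² and R² = v/(1 + v), on 130 df with no imbalance charge. At p = 0.078, power is 90.65%, 91.05% or 92.37% for D = 0.2, 0.5 or 1.0. At p = 0.086 it is 90.66%, 91.10% or 92.52%. Even a full SD adds less than 2 points.

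**Step 4: Aim 2.** 0.13 × 778.2/173.2 = 0.584, so 0.59 rests on the raw baseline SD, and the planned baseline adjustment already raises power: d = 0.59/√(1 − r²).

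| r | Planned, 62 per arm | Sex and age, R² = 0 | Sex and age, R² = 5% |
|---|---|---|---|
| 0.3 | 92.73% | 92.33–92.53% | 93.52–93.70% |
| 0.5 | 96.43% | 96.17–96.30% | 96.91–97.02% |
| 0.7 | 99.54% | 99.48–99.51% | 99.63–99.66% |

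At 67 per arm, planned power is 94.45%, 97.47% or 99.73%, and the R² = 5% gain is about 0.8 points or less.

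**Step 5: simulation for Aim 1.** 20,000 runs, N = 134, 11 women, permuted blocks of 4 within sex (block size assumed), r = 0.5. Type I error was 4.9–5.2% for the planned model and 5.0–5.3% with sex and age (Monte Carlo SE 0.15 points). With age R² of 0, 1, 2, 5 and 10%, power was 90.2, 90.4, 90.4, 90.6 and 90.6% as planned against 89.9, 90.4, 90.8, 91.6 and 93.1% adjusted (SE about 0.2). In a separate simulation with a 1 SD sex effect and a strong age effect, the planned model rejected 4.5% of the time under the null, which is slightly conservative.

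**The case against.** The case for leaving the plan alone is a fair one. The planned test is valid, and blocking already delivers the balance that stratification was meant to secure. Nothing in the documents shows that sex or age predicts either outcome beyond baseline. Two features suggest a small R²: Image Processing divides each map by its global mean, which removes person-to-person differences in global flow, and MRI Acquisition reports a test-retest intraclass correlation above 0.95, so baseline rCBF may already carry much of any stable sex or age difference (though that is not an 18-month correlation). With so few women, most of any gain must come from age, to which the stratification argument does not apply. The Covariates section does say that age and sex will be assessed. Changing a valid primary model late also has a cost in credibility.

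Most of this stands, and it is why the point is minor. It does not remove the point. Assessing a factor is not the same as naming it in the model, and the plan makes a definite commitment only for cognition. The possible loss is a fraction of a power point. The credibility cost arises only if the model changes after unblinding, which the fix avoids.

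**Conclusion.** The point holds and is minor. The randomisation stratum is absent from the Aim 1 and Aim 2 models, and nothing elsewhere in the document puts it there. There is no bias to correct, type I error is about 5% either way, and the sample size does not depend on the change. In Aim 1, adding sex and baseline age moves power by −0.4 to +2.5 points over an assumed partial R² of 0–10%, with 0.57 read as baseline-adjusted; the gain is smaller if 0.57 is on the raw scale. In Aim 2 the gain at R² = 5% is 0.1–1.0 points. Sex belongs in the model mainly so that the analysis matches the design; any real precision gain would come mostly from age. Fixing the timing and role of the other listed covariates is worth doing whatever the power figures show.

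**What to change.** Specific Aims describes the regional rCBF analyses in the past tense while Analyses uses the future, so first establish whether the data are still blinded.

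- **If blinded:** amend Analyses so that the Aim 1 and Aim 2 models contain treatment, the baseline outcome, sex (as the randomisation stratum) and baseline age. State in Covariates that every other listed factor enters at its baseline value only, in sensitivity models that do not replace the primary test.
- **If unblinded:** keep the treatment-plus-baseline model as primary and report the sex- and age-adjusted model as a sensitivity analysis.

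The cost is SAP wording and two degrees of freedom (131 to 129 in Aim 1, 121 to 119 in Aim 2), with a loss of about 0.2–0.4 power points in Aim 1 if sex and age explain nothing. No new data, visits or participants are needed.
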